12.6 STUDY TERMINATION AND SITE CLOSURE

Upon completion of the study, the following activities, when applicable, must be conducted by the Study Monitor in conjunction with the Investigator, as appropriate:

- Return of all study data to the Sponsor or its designee
- Data clarifications and/or resolutions
- Accounting, reconciliation, and final disposition of used and unused study drug
- Review of site study records for completeness; and
- Shipment of blood samples to the clinical laboratory.

Lupin Inc. reserves the right to temporarily suspend or prematurely terminate this study for any reason.

If the study is suspended or terminated for safety reason(s), Lupin Inc. will promptly inform the Investigator, and will also inform the regulatory authorities of the suspension or termination of the study and the reason(s) for the action. The Investigator is responsible for promptly informing the IRB/IEC, and providing the reason(s) for the suspension or termination of the study.

If the study is prematurely discontinued, all study data must be returned to the Sponsor or its designee. In addition, the site must conduct final disposition of all unused study drug in accordance with Lupin Inc. procedures for the study.

12.7 SITE TERMINATION

Lupin Inc. may, in its sole discretion, terminate a single study site for various reasons, including, but not limited to, the following:

- Failure of the Investigator to enroll subjects into the study at a reasonable rate
- Failure of the Investigator to comply with pertinent FDA regulations
- Submission of knowingly false information from the research facility to the Sponsor, Study Monitor, or FDA
- Insufficient adherence to protocol requirements

If the participation of a study site is terminated for reasons other than safety (e.g., uncorrected data acquisition or image quality issues), Lupin Inc. will issue a written notice to the Investigator. The written notice will contain the reasons for taking such action. If a study site is terminated for noncompliance, Lupin Inc. will also notify appropriate regulatory authorities. Study termination and follow up will be performed in compliance with the conditions set forth in 21 CFR 312.50 and 21 CFR 312.56.

12.8 RECORDS RETENTION

In accordance with applicable regulatory requirements and following completion or termination of the study, the Investigator will retain a copy of all study records in a safe, secure, and accessible location for a minimum of 2 years after notification by Lupin Inc. that the investigations have been discontinued, or for 2 years after all marketing applications have been approved. For EU submissions, retention of a minimum 5 years though it was post-submission is required. Study records will include at a minimum the following:

- Signed ICFs for all subjects
- Subject identification list
- Record of all communications between the Investigator and the IRB/IEC
- Record of all communications between the Investigator and the Sponsor or its designee
- List of all sub-investigators and other key study personnel
- Copies of all financial records related to the study including: financial arrangements for the study; financial payments made by the Sponsor or its designee to the Investigator; and financial interests held by the Investigator in the product or in Lupin Inc.
- Copies of CRFs for all subjects, and

- All other source documents (e.g., subject records, hospital records, laboratory reports, and drug accountability records, etc.)

To avoid any possible errors, the Investigator will contact Lupin Inc. prior to the destruction of any study records. The Investigator must immediately notify Lupin Inc. in the event of accidental loss or destruction of any study records.

12.9 CONFIDENTIALITY OF INFORMATION

Subject names will remain confidential and will not be supplied to the Sponsor or its designee. Only the subject number, subject initials, and birth date will be recorded in the CRF. If the subject name appears on any other document collected (e.g., hospital discharge summary), it must be obliterated from the document before the document is transmitted to the Sponsor or its designee. All study findings will be stored in electronic databases. The subjects will give explicit written permission for representatives of the Sponsor, regulatory authorities, and the IRB/IEC to inspect their medical records to verify the information collected. Subjects will be informed that all personal information made available for inspection will be handled in the strictest confidence and in accordance with all state, local, and federal data protection/privacy laws, including, without limitation, the HIPAA.

When subjects complete the study, all contact information will be purged from all study files, and all subject identifiers (other than an assigned subject number) will be obliterated from documentation confirming a clinical endpoint event.

12.10 PAYMENT TO SUBJECTS

Subjects may be compensated for participating in this study and the amount of payment will be stated in the ICF approved by the IRB/IEC.

12.11 CLINICAL TRIAL REGISTRATION

This clinical trial will be registered on the “clinicaltrials.gov” clinical trial registry website as required by 42 USC 282(j).

APPENDIX A - SOLOSEC PACKAGE INSERT

[figure not shown]

## DOCUMENT HISTORY

Rev No	Date	Description
1.0	10-Apr-2019	Original document
2.0	20-Mar-2020	Added clarification that the presence/absence of clinical symptoms of trichomoniasis is based on symptoms reported during the baseline vaginal assessment, with a sensitivity analysis if this differs from the randomized strata.

 PROSOFT Clinical	SEC-WH-301 Statistical Analysis Plan	Revision No.: 2.0
	Document Date: 20-Mar-2020	Page 4 of 12

## List of Abbreviations

AE	Adverse Event
BV	Bacterial Vaginosis
CMH	Cochran Mantel Haenszel
CRF	Case Report Form
EOS	End of Study
FDA	Food and Drug Administration
ITT	Intent to Treat
MedDRA	Medical Dictionary for Regulatory Activities
mITT	Modified Intent to Treat
NAAT	Nucleic Acid Amplification Testing
PP	Per-Protocol
SD	Standard Deviation
SOC	System Organ Class
TOC	Test of Cure
TV	Trichomonas Vaginalis
WHO	World Health Organization

	SEC-WH-301 Statistical Analysis Plan	Revision No.: 2.0
	Document Date: 20-Mar-2020	Page 7 of 12

## 1. INTRODUCTION

### 1.1 Study Background

Solosec® (secnidazole, SYM-1219) oral granules 2 grams is a Food and Drug Administration (FDA) approved treatment for bacterial vaginosis (BV) in adult women. Solosec™ is a potent, 5-nitroimidazole antibiotic with enhanced pharmacokinetic properties that enable delivery in a single dose that has been shown to be efficacious and well tolerated.

Trichomoniasis is the most prevalent nonviral sexually transmitted infection in the United States, affecting an estimated 3.7 million persons. Lupin is developing Solosec as an available treatment option to provide an alternative, effective, single dose therapy for women diagnosed with trichomoniasis that, in turn, should decrease the known serious sequelae that occur when this infection is left untreated or ineffectively treated.

### 1.2 Study Design

This is a Phase 3, multi-center, prospective, randomized, placebo-controlled, delayed treatment, double-blind, study to evaluate the effectiveness, and safety of a single, oral dose of Solosec containing 2 grams of secnidazole in female patients with trichomoniasis. Approximately 144 patients who test positive for trichomonas on OSOM® rapid test or via wet mount assessment or have positive *Trichomonas vaginalis* (*T. vaginalis*, TV) Nucleic Acid Amplification Testing (NAAT) within 30 days of screening (and have not been treated) and fulfill other eligibility criteria at the baseline visit will be enrolled in this study. The diagnosis of *T. vaginalis* will be confirmed by a positive culture for *T. vaginalis*.

The study will consist of a primary study phase (Visit 1 (baseline) to Visit 2 (Day 6-12)) and a follow-up phase (Visit 2 to Visit 3 (7-12 days post Visit 2)). During the primary phase patients will be randomly assigned in a 1:1 ratio to either Solosec or placebo. The randomization will be stratified by site and based on the clinical symptoms of trichomoniasis (present or absent).

Patients will return to the clinic for the “test of cure” (TOC) visit to be conducted on Days 6-12 (Visit 2). After all Visit 2 (V2) study procedures have been completed, patients will receive the opposite treatment (placebo patients will receive Solosec and vice versa). Patients with V2 cultures that are subsequently positive for *T. vaginalis* will return to the clinic for Visit 3 (V3) assessments and investigator assessment of need for additional therapy (an additional Visit 4 may be scheduled at the investigator’s discretion if culture at V3 is positive). Patients with

	SEC-WH-301 Statistical Analysis Plan	Revision No.: 2.0
	Document Date: 20-Mar-2020	Page 8 of 12

cultures that are negative at V2 will be contacted by phone and discharged from the study (no V3 required).

### 1.3 Study Objectives

#### 1.3.1 Primary Objectives

The objective of this study is to evaluate the efficacy and safety of a single, oral dose of Solosec containing 2 grams of secnidazole compared to placebo for the treatment of trichomoniasis.

#### 1.3.2 Secondary Objectives

None.

## 2. STATISTICAL METHODOLOGY

### 2.1 General Principles

All analyses will be performed using SAS® software version 9.4. Prior and concomitant medications will be coded using World Health Organization (WHO) Drug Dictionary Enhanced March 2019. Medical history and Adverse Events (AEs) will be coded using Medical Dictionary for Regulatory Activities (MedDRA) version 22.0.

Continuous variables will be summarized by n (number of patients with non-missing results), mean, standard deviation (SD), median, minimum, and maximum. Categorical variables will be summarized by count and percent (of patients in the population with a non-missing result).

All data collected will be presented in data listings. Data collected subsequent to TOC (Visits 3 and 4) will be included in data listings but will not be used for any analyses.

### 2.2 Sample Size Determination

Assuming a responder rate (microbiological cure) of 75% in the Solosec treatment group and a 40% placebo response rate and based on the use of a two-sided, two-sample comparison of proportions at the alpha=0.05 level of significance, a sample size of 100 patients (50 patients in each group) who meet the mITT criteria will provide approximately 95% power to demonstrate a statistically significant difference between Solosec and placebo. Assuming 70% of patients randomized in the study will meet the mITT criteria, approximately 144 patients will be enrolled into the study.

	SEC-WH-301 Statistical Analysis Plan	Revision No.: 2.0
	Document Date: 20-Mar-2020	Page 9 of 12

## 2.3 Study Populations

**Intent-to-Treat (ITT):** The ITT population will include all randomized patients. Patients will be summarized based on the randomized treatment group.

**Modified Intent-To-Treat (mITT):** The mITT population will include all randomized patients who were culture positive for *T. vaginalis* and negative for STIs (lab results will not be known until after randomization). Patients will be summarized based on the randomized treatment group.

**Per-Protocol (PP):** The PP population will be composed of patients in the mITT population with consideration of the following criteria: received the study medication as randomized, met inclusion and exclusion criteria, had a TOC visit between Days 6-12, and had no major protocol violations. The composition of the PP population will be finalized and documented in a review of the data conducted prior to unblinding the study database.

**Safety:** The Safety population will be composed of all randomized patients who received any amount of study medication. Patients will be summarized based on the treatment group actually received.

## 2.4 Patient Accounting and Baseline Characteristics

Demographics will be summarized by treatment group for the mITT, PP, and safety populations. Other baseline characteristics (vaginal assessments, vital signs, laboratory results, medical history) and prior and concomitant medications will be summarized by treatment group for the safety population. Study completion status and primary reason for discontinuation will be displayed by treatment group for the ITT population.

## 2.5 Efficacy Analyses

The mITT population will be the primary efficacy population. The primary and exploratory efficacy analyses will also be conducted on the PP population. The presence/absence of clinical symptoms of trichomoniasis are based on symptoms reported during the baseline vaginal assessment.

### 2.5.1 Primary Efficacy Analyses

The primary efficacy endpoint, Microbiological Cure (i.e., InPouch™ TV test negative for *T. vaginalis*) at the TOC Visit (Study Day 6-12), will be compared between the active and placebo treatment groups using a two-sided Cochran-Mantel-Haenszel (CMH) test (stratified by the presence/absence of clinical symptoms of trichomoniasis at baseline) at the alpha=0.05 level of

	SEC-WH-301 Statistical Analysis Plan	Revision No.: 2.0
	Document Date: 20-Mar-2020	Page 10 of 12

significance. In the event that there are subjects whose actual symptom strata differs from the strata used for randomization, a sensitivity analysis will be conducted using the randomized strata to assess the impact of the strata differences.

### **2.5.2 Additional Analyses of Primary Endpoint**

For each treatment group, an exact 95% binomial confidence interval of the cure rate will be calculated. Within each stratum, cure rates will be compared between the active and placebo treatment groups using a two-sided Fisher's exact test.

### **2.5.3 Exploratory Efficacy Analyses**

The exploratory endpoint, Outcome Responder, will be evaluated at the TOC Visit (Study Day 6-12) for the subgroup of patients who have clinical symptoms of trichomoniasis at baseline. A patient is considered a responder if they have complete resolution of trichomoniasis symptoms (i.e., itching, discharge, and odor recorded as normal) and culture results (InPouch™ TV test) negative for *T. vaginalis*. Outcome Responders will be compared between the active and placebo treatment groups using a two-sided Fisher's exact test. For each treatment group, an exact 95% binomial confidence interval of the responder rate will be calculated.

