9.4.7 Vaginal Discharge Assessment

During the pelvic examination, conduct clinical assessment of trichomoniasis symptoms (e.g., itching, discharge, odor) (record as Normal, or Abnormal consistent with TV, or Abnormal Other).

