11.5 STUDY ENDPOINT ANALYSES

11.5.1 Efficacy Analyses

Primary Efficacy Analysis

The primary efficacy endpoint, Microbiological Cure (i.e., InPouch™ TV test negative for *T. vaginalis*) at the TOC visit (Study Day 6-12), will be compared between the active and placebo treatment groups using a two-sided Cochran-Mantel-Haenszel (CMH) test (stratified by the presence/absence of clinical symptoms of trichomoniasis at baseline) at the alpha=0.05 level of significance.

Exploratory Efficacy Analyses

The following exploratory endpoint will be evaluated at the TOC Visit (Study Day 6-12) for the subgroup of patients who have clinical symptoms of trichomoniasis at baseline:

- **Outcome Responder:** complete resolution of trichomoniasis symptoms (i.e., itching, discharge, and odor recorded as normal) and culture results (InPouch™ TV test) negative for *T. vaginalis*

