### **2.6.1 Adverse Events**

AEs that occur through the TOC Visit will be summarized by System Organ Class (SOC), Preferred Term, intensity, and treatment group for treatment-emergent AEs. Summaries will also be provided for study drug-related AEs, serious AEs, and AEs leading to study discontinuation. Each patient will be counted only once for each of the incidence rates, regardless of the number of occurrences (events) the patient experiences.

A Treatment-emergent AE is defined as any AE that occurs after administration of the study drug and through the final visit, or any event that is considered study drug-related regardless of the start date of the event.

	SEC-WH-301 Statistical Analysis Plan	Revision No.: 2.0
	Document Date: 20-Mar-2020	Page 11 of 12

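### Does the exploratory symptom endpoint need a planned split between findings attributed to trichomonas and findings attributed to another cause?

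*SAP*

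**What the plan says.** Protocol 9.4.7 gives the scale for the clinical assessment of itching, discharge and odor: "record as Normal, or Abnormal consistent with TV, or Abnormal Other". The assessment is made at baseline and again at the test-of-cure (TOC) visit (protocol Table 1 and 9.3.2).

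Protocol 11.5.1 defines Outcome Responder, in patients symptomatic at baseline, by "complete resolution of trichomoniasis symptoms (i.e., itching, discharge, and odor recorded as normal) and culture results" negative for the organism. SAP 2.5.3 repeats the definition, with the symptom part again given as "complete resolution of trichomoniasis symptoms (i.e., itching, discharge, and odor recorded as normal", and adds a two-sided Fisher's exact test and an exact 95% confidence interval per arm. SAP 2.5 repeats the analysis in the per-protocol population, and SAP 3.2 counts unknown status as non-response.

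Four other parts of the SAP bear on the point:

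- Section 2.5.2, on culture alone: "Within each stratum, cure rates will be compared between the active and placebo treatment groups".
- Section 2.6.1: "AEs that occur through the TOC Visit will be summarized by System Organ Class (SOC), Preferred Term, intensity, and treatment group".
- Section 2.4: "prior and concomitant medications will be summarized by treatment group for the safety population". Vaginal assessments are summarized in the same section, but only as baseline characteristics.
- Section 2.1: "All data collected will be presented in data listings".

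**The concern.** The endpoint's name refers to symptoms of trichomoniasis, while its rule asks for every named symptom to be normal whatever the cause. The protocol provides a category that separates TV from other causes, and the analysis then merges the two abnormal categories. A culture-negative patient with a finding that the investigator attributes elsewhere is counted like one whose TV symptoms persist.

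Such findings are foreseeable. Women with bacterial vaginosis are eligible (protocol 6.2), and Solosec is approved to treat that condition (protocol 3.2.1). In the bacterial vaginosis studies, yeast infections were more common on Solosec than on placebo (also 3.2.1). The first could favor the active arm on this endpoint and the second could count against it. Neither is documented as what the Abnormal Other category contains; both are inferred.

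At stake is the reading of the plan's only efficacy analysis of symptoms. A modest responder rate on Solosec could mean residual TV symptoms or unrelated findings, and the planned tables would not say which.

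**Working it through.** **1. The plan's own figure.** SAP 2.2 states: "Assuming a responder rate (microbiological cure) of 75% in the Solosec treatment group and a 40% placebo response rate". With 50 per arm, two-sided alpha 0.05 and a pooled variance:

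- Mean proportion = (0.75 + 0.40)/2 = 0.575; 2 × 0.575 × 0.425 = 0.48875.
- z = [0.35 × √50 − 1.96 × √0.48875] / √(0.75 × 0.25 + 0.40 × 0.60) = (2.475 − 1.370)/0.654 = 1.69.
- Power = 95.4%, matching the stated 95%. The unpooled approximation gives 96.6% and exact Fisher enumeration 93.4%.
- Enrolment: 50/0.70 = 71.4, so 72 per arm and 144 in total, as stated.

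These figures concern culture cure only. The documents give no rate, power or sample size for Outcome Responder.

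**2. Name against rule.** Protocol Table 1, 9.3.1, 9.3.2 and 9.4.7 all use the phrase about trichomoniasis symptoms as the name of the items examined, with itching, discharge and odor as examples. Section 9.4.7 then allows that same assessment to be graded as abnormal for another reason, so the name carries no attribution of cause. Read this way, the parenthesis in the responder definition simply states the rule: the named items are normal. Protocol and SAP agree, and two analysts would code it identically.

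**3. What the planned output shows.** Culture cure in the symptomatic stratum (SAP 2.5.2), set beside Outcome Responder (2.5.3), gives the number of culture-negative patients who fail on symptoms or on missing symptom data. Adverse-event and medication summaries may show yeast infection or its treatment by arm, without a link to responder status. The symptom category at TOC appears in the listings only. The split is therefore not tabulated, but it can be counted.

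**4. Illustrative size.** Let c be the culture cure rate and f the share of culture-negative symptomatic patients whose only abnormal findings at TOC are graded Abnormal Other. The strict responder rate is lower than a rate that tolerates those findings by c × f. Assume c = 75% and 40% in the symptomatic subgroup, and f between 5% and 20% in each arm. No value of f is given in the documents.

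- Solosec: 75 × 0.05 = 3.75 points to 75 × 0.20 = 15.0 points.
- Placebo: 40 × 0.05 = 2.0 points to 40 × 0.20 = 8.0 points.
- Change in treatment difference = −(75 × f on Solosec − 40 × f on placebo):

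| f Solosec | f placebo | Change (points) |
|---|---|---|
| 5% | 5% | −1.75 |
| 10% | 10% | −3.5 |
| 20% | 20% | −7.0 |
| 20% | 5% | −13.0 |
| 5% | 20% | +4.25 |

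The change is zero when f on placebo is 75/40 = 1.875 times f on Solosec. The sign is open.

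**5. Precision of the endpoint.** Assume 25 symptomatic patients per arm and that 10% of culture-negative patients keep TV-type findings. With no Abnormal Other findings at all, the responder rates are 0.75 × 0.90 = 67.5% and 0.40 × 0.90 = 36.0%, and Fisher power is only 55%. If f is 30% on Solosec and 10% on placebo, the difference is 13.0 points and power 11%. Reversed, it is 36.0 points and 68%. The comparison is imprecise under any definition, and one reclassified patient moves an arm's rate by 1/25 = 4 points.

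**The case for a change.** The strongest argument for a change is that attribution matters on entry but not in the outcome. Protocol 4.3.2 describes the subgroup by symptoms attributable to trichomoniasis, yet a symptom attributed elsewhere at TOC counts as failure. A count taken from listings after unblinding is post hoc, whereas a short table specified now would not be. The rating is made double-blind and before the Visit 2 culture result is known, so it is not obviously biased. The data would come from an assessment already scheduled.

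Part of this stands: no planned table gives the split, and a descriptive one would do no harm. It does not amount to a fault in the plan, for three reasons.

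- **Softer data.** At Visit 2 no whiff test, pH or wet mount is scheduled, and the culture result is pending. Separating TV from other causes is then clinical judgement alone. Requiring all three symptoms to be normal avoids that judgement.
- **Design limits.** Exclusion criteria 2 and 4 keep out suspected alternative causes of symptoms and conditions that could confound the clinical response. The mITT population also drops patients positive for other sexually transmitted infections. Bacterial vaginosis and yeast arising after dosing remain possible.
- **Unverified fields.** Protocol 9.4.7 does not say whether the three-level grade is recorded for each symptom or once overall. Whether the proposed split can be built for each symptom depends on the case report form, which the documents do not show.

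**Conclusion.** The concern does not call for a change. Outcome Responder has one explicit rule, worded alike in both documents, and the planned test and intervals estimate it properly. Choosing all-normal over an attribution-based rule is a fair trade-off: it is stricter and mixes causes, but it does not depend on an untested judgement at Visit 2. What is left is a descriptive breakdown that some readers would like, and analysts can supply it from the listed data if the result prompts the question.

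The possible effect, -13.0 to +4.25 points on the treatment difference, rests wholly on an assumed 5% to 20% frequency of Abnormal Other findings and on the planned cure rates holding among symptomatic patients. The documents support neither a likely value nor a direction. The endpoint is exploratory, so the primary culture analysis, its alpha and the sample size stay as they are.
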